4.3 Exclusion Criteria

Patients who meet any of the following criteria by the end of screening period will be excluded from the study.

1. Patients who have progressive disease (PD) on RECIST version 1.1 at the end of at least 4 cycles of first-line platinum-containing chemotherapy.
2. Patients who are judged to have clinically progressive symptoms at the end of at least 4 cycles of first-line platinum-containing chemotherapy by the investigator or subinvestigator.
3. (deleted)
4. Patients with a history of malignant cancer (except for carcinoma in situ or intra-mucosal cancer that resolved with endoscopic therapy) within 5 years before enrollment.
5. Patients who received any prior therapies for target disease within 3 weeks before the first administration of S-588410.
6. Patients who cannot receive the first administration of S-588410 within 12 weeks

-
- after the last administration of chemotherapy.
7. Patients who are expected to require any of the following therapies between enrollment and completion or discontinuation of the study treatment.
 - Anti-malignant tumor drug
 - Systemic corticosteroid (except for corticosteroid defined as the equivalent of prednisone ≤ 10 mg/day orally)
 - Systemic immunosuppressant drug
 - Immunotherapy
 - Radiotherapy (except for restricted radiotherapy for pain relief of bone metastasis) for the target disease
 - Surgical therapy for the target disease
 - Hyperthermia for the target disease
 - Herbal medicine with anti-tumor or immunosuppressant effect
 - Other investigational new products
 8. Patients who have severe (CTCAE version 4.03 grade 3 or higher) concurrent hepatic impairment, renal impairment, heart disease, hematological disease, respiratory disease, or metabolic disease, with the exception of any symptoms and/or signs associated with target disease.
 9. Patients who have the following laboratory data with grade 3 or higher according to CTCAE version 4.03 criteria within 28 days before enrollment.
 - White blood cell count $<2000/\text{mm}^3$ or $>100\,000/\text{mm}^3$
 - Platelet count $<50\,000/\text{mm}^3$
 - Hemoglobin <8.0 g/dL
 - Aspartate aminotransferase (AST) or alanine aminotransferase (ALT) $>5.0 \times$ the upper limit of normal (ULN)
 - Total bilirubin $>3.0 \times$ ULN
 - Serum creatinine $>3.0 \times$ ULN

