 21. Patients who received any other investigational products within 28 days or 5 half-lives of the investigational products before enrollment whichever is longer.
 22. Patients who are considered ineligible for this study by the investigator or subinvestigator due to any reasons, including inability to understand and follow the requirements of the study.

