7.6.8 Serious Adverse Events

7.6.8.1 Definition

An SAE is defined by regulation as any AE occurring at any dose that results in any of the following outcomes:

- death
- life-threatening condition
- hospitalization or prolongation of existing hospitalization
- persistent or significant disability/incapacity
- congenital anomaly/birth defect
- other medically important condition.

Important medical events that may not result in death, be life threatening, or require hospitalization may be considered as SAE when, based upon appropriate medical judgment, they may jeopardize the patient and may require medical intervention to prevent one of the outcomes listed in this definition. Examples of such medical events include allergic bronchospasm requiring intensive treatment in an emergency room or at home, blood dyscrasias or convulsions that do not result in inpatient hospitalization, or the development of drug dependency or drug abuse. The investigator or subinvestigator will determine the seriousness of AEs.

For the following criteria, termed “Hy’s law“, shown in the management and discontinuation criteria for liver function abnormalities ([Appendix 3](#)), the case must be reported as an SAE.

- AST or ALT $>3 \times$ ULN and total bilirubin $>2 \times$ ULN or PT-INR >1.5

Aggravation of target disease (eg, tumor growth and the appearance of new lesion) or any symptoms and/or signs associated with target disease (eg, cancer pain and carcinomatous pleural effusion) result in any of the outcomes such as death or life-threatening condition, they must be reported as SAEs.

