Appendix 3 Management and Discontinuation Criteria for Abnormal Liver Function Tests

Management and Discontinuation Criteria for Abnormal Liver Function tests have been designed to ensure patient safety and evaluate liver event etiology. (See Guidance for Industry Drug-Induced Liver Injury: Premarketing Clinical Evaluation, FDA: 2009)

Abnormal Liver Chemistry Criteria:

The investigator or subinvestigator must review study patient laboratories to identify if any levels meet the following criteria:

- a. AST or ALT $>5 \times$ ULN
- b. AST or ALT $>3 \times$ ULN and total bilirubin $>2 \times$ ULN or PT-INR >1.5 , if PT-INR measured.
- c. AST or ALT $>3 \times$ ULN with signs or symptoms compatible with hepatitis or hypersensitivity (eg, fatigue, nausea, vomiting, right upper quadrant pain or tenderness, jaundice, fever, rash, eosinophilia [$>5\%$])

Action to be taken by Investigator:

If any of abnormal liver chemistry criteria is met, the investigator or subinvestigator must do the following:

- Patients must be instructed to hold study medication immediately. The investigator or subinvestigator should not re-challenge the patient with the investigational product without consulting the sponsor.
- Following the initial observed elevation, every effort should be made to have the patient return to the clinic within 48 to 72 hours to repeat liver function chemistries and for further hepatic evaluation.
- Patients must be monitored 2 to 3 times per week until liver function chemistries (ALT, AST, ALP, total bilirubin) resolve, stabilize or return to within the normal range or to baseline levels.
- This event must be reported to the sponsor within 72 hours of learning after its occurrence on the Liver Event Form (refer to [7.6.8.2](#), for reporting destination).
- Consultation with a specialist such as a hepatologist is considered.
- Liver imaging (ie, ultrasound, MRI, CT) is considered.
- For criteria b, termed “Hy’s law“, the case must be reported as an SAE.

Follow-up Examination:

If any of abnormal liver chemistry criteria are met, the following assessments should be performed at the follow-up visit(s) and documented in the Liver Event Form:

- Clinical symptoms course

- Concomitant medications: OTC/herbal/dietary supplements (start and stop dates)
- Alcohol use
- Risk factors for nonalcoholic steatohepatitis (NASH) such as diabetes, obesity and hypertriglyceridemia
- Autoimmune hepatitis/cholangitis
- Wilson's disease
- Laboratory Assessments

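### Exclusion 9 admits patients who already meet the bilirubin arm of Appendix 3 criterion b, so unchanged values on treatment force a hold

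*Protocol*

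**What the plan says.** **Entry.** Exclusion 9 in 4.3, repeated in the synopsis, opens with "Patients who have the following laboratory data with grade 3 or higher according to CTCAE version 4.03 criteria within 28 days before enrollment" and then lists each test on its own line. The two liver lines are AST or ALT above 5.0 × ULN, and "Total bilirubin $>3.0 \times$ ULN". No line combines them. Two other exclusions touch the liver. Exclusion 8 covers "Patients who have severe (CTCAE version 4.03 grade 3 or higher) concurrent hepatic impairment" and sets aside findings due to the target disease. Exclusion 22 covers "Patients who are considered ineligible for this study by the investigator or subinvestigator due to any reasons".

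**On treatment.** Criterion b of Appendix 3 reads "AST or ALT $>3 \times$ ULN and total bilirubin $>2 \times$ ULN or PT-INR >1.5 , if PT-INR measured". When any of criteria a, b or c is met, the first required action is "Patients must be instructed to hold study medication immediately". If criterion b is confirmed on repeat testing, the patient must be discontinued whatever the history, except where the investigator attributes the values to the target disease and sees no need to stop. For the same combination, which the protocol terms Hy's law, 7.6.8.1 states that "the case must be reported as an SAE", and Appendix 3 repeats this.

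**Adverse event definitions.** Section 7.6.1 describes AEs as occurrences that are new, or worse than at baseline. Section 7.6.7 opens with results that are worsening from baseline, and then lists meeting the Appendix 3 criteria among the circumstances that make a result clinically significant. Under 7.6.11, an AE reported after the first dose in the S-588410 Group is a TEAE.

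**The concern.** Entry and stopping limits should be read together. A patient who passes screening should not meet a mandatory stopping rule on the same values. Here the entry limits are set test by test and criterion b is set on the pair, at lower multiples of ULN. The protocol can therefore enrol someone whom it must immediately take off the drug although nothing has happened since screening.

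At stake are a vaccination course interrupted or ended for a pre-existing finding, and a safety report that may describe a screening value as a serious event on treatment. A patient in the range that the protocol itself labels Hy's law is also a doubtful candidate for a first dose.

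**Working it through.** The plan gives no figure on this point, so the check compares thresholds.

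**Inputs (multiples of ULN)**

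| Rule | AST/ALT | Total bilirubin |
|---|---|---|
| Exclusion 9: excluded if | above 5.0 | or above 3.0 |
| So permitted at entry | up to 5.0 | and up to 3.0 |
| Appendix 3 criterion a: met if | above 5 | not used |
| Appendix 3 criterion b, bilirubin arm: met if | above 3 | and above 2 |

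**Step 1: overlap.** Permitted at entry and meeting criterion b means AST/ALT above 3 and up to 5.0, together with bilirubin above 2 and up to 3.0. Example: AST 4 and bilirubin 2.5. Since 4 ≤ 5.0 and 2.5 ≤ 3.0, exclusion 9 does not apply. Since 4 > 3 and 2.5 > 2, criterion b is met.

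**Step 2: do other rules close the gap?** Exclusion 8 starts at grade 3, as exclusion 9 does. Exclusion 22 allows the investigator to refuse the patient but does not require it. The gap stays open by rule.

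**Step 3: compare criterion a.** Its limit, above 5 × ULN, equals the AST/ALT limit of exclusion 9, so no eligible patient meets it at entry. Criterion b has no matching entry limit.

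**Step 4: consequences with unchanged values.**
- Hold: required. The trigger is any criterion met, in absolute multiples of ULN. Among the required actions, baseline appears only as a possible end point for monitoring.
- Discontinuation: required once confirmed, subject to the target-disease exception. That exception covers discontinuation only. Restart is open only to patients who do not meet a discontinuation criterion.
- SAE report: required by the Hy's law sentences in 7.6.8.1 and Appendix 3. Against this, 7.6.8.1 defines an SAE as a kind of AE, 7.6.1 asks for something new or aggravated, and 7.6.7 opens with worsening results. The text does not decide between the two.

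**Step 5: size if it were counted.** One case among the planned 42 would read as 1/42 = 2.4% in the serious TEAE row of 8.10.1. It would probably be judged not related under 7.6.4 and so stay out of the ADR summary.

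**Step 6: after adding the combined exclusion.** Entry would bar AST/ALT above 3.0 together with bilirubin above 2.0, which is the bilirubin arm of criterion b, so the overlap in Step 1 is empty. Criterion c (AST/ALT above 3 × ULN with signs such as fatigue or eosinophilia) could still be met by an eligible patient at 3 to 5 × ULN. The PT-INR arm could too, since PT-INR is not in Table 7-2.

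**Step 7: sample size, for context.** Exact one-sided binomial test, null rate 0.5, level 0.05, true rate 0.75:
- n = 35: reject at 23 or more, actual level 0.0448, power 92.4%, in line with the 90% claimed in 8.2.
- n = 41: reject at 27 or more, power 93.3%.
- n = 42: reject at 27 or more, power 95.8%.

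One evaluable patient fewer does not threaten the 90%. A patient excluded at screening does not reduce the 42 to be enrolled.

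**The case against.** The best reply is that Appendix 3 is written for new events. It speaks of an elevation first observed, of an event and its occurrence, and lets monitoring end when values stabilise or return to baseline. Read with 7.6.1 and the opening of 7.6.7, an unchanged value is not an AE and so neither an SAE nor a TEAE. If the criteria are instead applied to the screening results, the hold falls before the first dose and no TEAE arises. This stands against a stronger inference that a reader might draw, namely that such a patient will certainly inflate the serious TEAE count. Nor does the list in 7.6.7 settle the matter, because it refers back to results introduced as worsening.

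The reply does not remove the mismatch. The hold does not depend on AE status, and nothing in Appendix 3 exempts values present at entry. If the hold falls before dose one, the protocol has enrolled a patient who may not be dosed.

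A second reply is that tighter limits on study than at entry are a cautious choice, and that exclusion 8 and the discontinuation rule both make room for disease-related abnormality, which the added line would not. The caution is fair, and the rules do err on the safe side. But exclusion 9 already has no target-disease exemption, so a further line without one fits its form. The loss of some disease-related cases is a real cost.

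**Conclusion.** The overlap is real and follows from the stated thresholds alone. The hold, and discontinuation once confirmed subject to the target-disease exception, follow from Appendix 3 as written. The SAE report is stated outright but conflicts with the general AE definitions, so its place in the TEAE tables is open.

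The magnitude is low. The protocol gives no frequency for this combination, and it may be zero. Two further readings are not supported. One is that liver injury could be missed: the rules stop dosing rather than allow it. The other is that the proposed line makes all entry and stopping limits agree: it does so for the bilirubin arm of criterion b, as already holds for criterion a, but not for criterion c or the PT-INR arm. Power and the primary endpoint are unaffected. This is a cheap improvement. The verdict assumes that Appendix 3 applies to unchanged values, as its unconditional trigger says.

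**What to change.** Add one line to exclusion 9, in 4.3 and in the synopsis: *or, regardless of grade, AST or ALT >3.0 × ULN together with total bilirubin >2.0 × ULN*. The words on grade are needed because the lead-in otherwise restricts the list to grade 3 or higher.

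Leave the triggers in Appendix 3 and 7.6.8.1 as absolute limits, including criterion c and the PT-INR arm. They remain useful as on-study precautions, and making them relative to baseline would loosen a safety rule.

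The cost is one line in two places. No new test is needed, since AST, ALT and total bilirubin are in the routine panel already taken at screening. The downside is that a few borderline patients become ineligible, including some whose values come from the cancer itself.

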 - Viral hepatitis serology
 - Hepatitis A IgM antibody
 - Hepatitis B surface antigen and Hepatitis B core antibody (IgM)
 - Hepatitis C RNA
 - Hepatitis E IgM antibody
 - Cytomegalovirus IgM antibody
 - Epstein-Barr viral capsid antigen IgM antibody
 - For patients with total bilirubin of >1.5 ULN, conjugated bilirubin should be measured
 - Complete blood count with differential to assess for eosinophilia

Re-starting Study Medication Criteria

For patients that meet the abnormal liver chemistry criteria, but only if they do not meet the "Drug Discontinuation Criteria Due to Abnormal Liver Chemistry Tests" may re-start the administration of study drug.

For patients with ALT $>5 \times$ ULN to $\leq 8 \times$ ULN with elevations for less than two weeks, the study drug may be re-started at the discretion of the investigator and sponsor if both of the following conditions are met:

- Subsequent liver function chemistries are lower or unchanged
- No signs or symptoms consistent with hepatitis or hypersensitivity (eg, fatigue, nausea, vomiting, right upper quadrant pain or tenderness, jaundice, fever, rash or eosinophilia [$>5\%$])

All patients that have met abnormal liver chemistry criteria must still be monitored 2 to 3 times per week until liver function chemistries (ALT, AST, alkaline phosphatase, and total bilirubin) resolve, stabilize or return to within the normal range or to baseline levels.

Drug Discontinuation Criteria Due to Abnormal Liver Chemistry Tests

Patients must be discontinued from the study as described below except that the investigator judges abnormal liver chemistry test values are due to target disease and discontinuation is not necessary:

- AST or ALT $>8 \times$ ULN, confirmed by follow-up testing (ie, initial abnormality is confirmed on subsequent testing), regardless of medical history or physical examination findings
- AST or ALT $>5 \times$ ULN, with elevations for more than 2 weeks or development of

concomitant signs or symptoms consistent with hepatitis or hypersensitivity (eg, fatigue, nausea, vomiting, right upper quadrant pain or tenderness, jaundice, fever, rash or eosinophilia [$>5\%$])

- AST or ALT $>3 \times$ ULN and total bilirubin $>2 \times$ ULN or PT-INR >1.5 , if PT-INR measured, confirmed by follow-up testing (ie, initial abnormality is confirmed on subsequent testing), regardless of medical history or physical examination findings.

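### Appendix 3 holds and stops drug on AST or ALT, but its conditional restart rule names ALT only, so a rising isolated AST does not bar restart

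*Protocol*

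**What the plan says.** The liver rules in Appendix 3 of the protocol come in three layers.

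- **Hold.** Criteria a, b and c each trigger an immediate hold, and each is written for either enzyme; the first is "a. AST or ALT $>5 \times$ ULN". The investigator "should not re-challenge the patient with the investigational product without consulting the sponsor".
- **Restart.** A general sentence covers any patient who met a hold criterion but no discontinuation criterion: such a patient "may re-start the administration of study drug". A second paragraph then reads "For patients with ALT $>5 \times$ ULN to $\leq 8 \times$ ULN with elevations for less than two weeks, the study drug may be re-started". It leaves the decision to investigator and sponsor jointly and attaches two conditions, both of which must hold. One is "Subsequent liver function chemistries are lower or unchanged"; the other is the absence of signs or symptoms of hepatitis or hypersensitivity.
- **Discontinuation.** There are five criteria, again all for either enzyme. They include "AST or ALT $>8 \times$ ULN, confirmed by follow-up testing" and "AST or ALT $>5 \times$ ULN, with elevations for more than 2 weeks or development of" such signs or symptoms. They apply unless the investigator attributes the values to the target disease and judges discontinuation unnecessary.

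**The concern.** The two transaminases are treated alike everywhere in Appendix 3 except in the conditional restart paragraph, and no reason is given for the exception. The requirement that repeat values not be rising appears only there, and only an ALT value triggers it. A patient with an isolated AST elevation is therefore governed by the general restart sentence, which says nothing about the direction of the retest.

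The rule decides re-exposure to S-588410 after a liver signal. Section 1.3 says the five-peptide product has not been studied in humans, although its component peptides have. A rising enzyme is a plain reason not to re-dose yet, and the protocol makes it a bar for one of the two markers only.

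**Working it through.** No sample size, error rate or estimate is involved. The check is a count of the rules and a trace of paired cases through them.

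**Rule count (Appendix 3)**

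| Layer | Rules | AST or ALT | ALT only |
|---|---|---|---|
| Hold criteria | 3 | 3 | 0 |
| Discontinuation criteria | 5 | 5 | 0 |
| Conditional restart | 1 | 0 | 1 |
| Total | 9 | 8 | 1 |

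**Paired cases.** In each pair one enzyme is raised alone: AST in one patient, ALT in the other. Assumed values: first result 6 × ULN, one week's duration, bilirubin and PT-INR not raised, weekly follow-up possible, values not attributed to the target disease, sponsor consulted. The restart section is read so that the ALT paragraph limits the general sentence for the patients it names.

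| Symptoms | Retest (× ULN) | Isolated AST | Isolated ALT |
|---|---|---|---|
| No | 5.5 | restart allowed | restart allowed |
| No | 6 | restart allowed | restart allowed |
| No | 7.5 | **restart allowed** | **restart not allowed** |
| No | 8.5, confirmed | discontinued | discontinued |
| Yes | 5.5, 6, 7.5 or 8.5 confirmed | discontinued (all four) | discontinued (all four) |

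**Trace of the pair that differs**

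1. At 6 × ULN, hold criterion a is met for either enzyme.
2. At 7.5 × ULN, asymptomatic and within two weeks, no discontinuation criterion is met. The value is not above 8 × ULN, has not lasted more than two weeks, comes without symptoms, has no bilirubin or PT-INR rise, and weekly follow-up is possible.
3. The general sentence therefore permits restart.
4. For ALT, 7.5 lies between 5 and 8 × ULN, so the conditional paragraph applies. Since 7.5 > 6, the retest condition fails.
5. For AST, the conditional paragraph is not triggered, so the rise has no effect on restart.

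One of the eight pairs differs. The uncovered region is isolated AST above 5 and up to 8 × ULN, rising, asymptomatic and present for less than two weeks. If ALT is also in the 5 to 8 × ULN range, the paragraph is triggered and its retest condition, which refers to liver chemistries generally, catches a rising AST too.

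**The case against.** The strongest objection is that the restart section can be read in more than one way. Both sentences are permissive, and nothing states that the second limits the first.

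- If the general sentence stands alone, a rising ALT may restart as well and the enzymes do not differ. That reading leaves the two ALT conditions with no effect.
- If the general sentence states only a necessary condition, an isolated AST above 5 × ULN has no express restart route and the gap is conservative. That reading also strands patients held at above 3 to 5 × ULN who meet no discontinuation criterion, although the general sentence expressly covers them.
- The reading used here, in which the second paragraph limits the first for ALT, avoids both problems.

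The contrast in the 7.5 × ULN row does depend on this choice. On every reading, though, the retest condition does not reach an isolated AST.

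The second objection is that existing controls leave little exposed. Drug is held at once, a repeat test is sought within 48 to 72 hours, the event is reported to the sponsor within 72 hours, and monitoring two to three times a week names AST. A continued rise ends in discontinuation. After week 12, dosing is every two weeks, so the next scheduled dose falls at about the time the two-week rule takes over. All of this stands and keeps the point minor. It does not close the gap. Sponsor consultation sets no criterion on trend, and none of the level, duration or symptom rules addresses a value that is rising between 5 and 8 × ULN in the first two weeks. The weekly dosing phase remains exposed.

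The third objection is that one in eight is not a risk. That is right: the cases were chosen to map the rules, and the fraction says nothing about frequency.

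**Conclusion.** The concern holds as a minor patient-safety inconsistency in wording. Eight of the nine enzyme-based rules cover both transaminases, and the one that makes a rising retest a bar to restart covers ALT only. The consequence is confined to an isolated, asymptomatic, rising AST between 5 and 8 × ULN within two weeks, with sponsor consultation as the remaining check before re-dosing. The difference in outcome between the enzymes assumes that the ALT paragraph limits the general restart sentence. The failure of the retest condition to reach isolated AST does not need that assumption. The protocol gives no rate of such elevations, so no patient count can be derived. The primary endpoint, its test, the sample size, the withdrawal rules and endpoint follow-up are unaffected.

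**What to change.** In Appendix 3, under the re-starting criteria, change the opening of the second paragraph so that it applies to AST or ALT above 5 and up to 8 × ULN. Add a clause stating that the paragraph's two conditions limit the general restart sentence for patients in that range, which also settles the ambiguity of reading described above. The cost is the wording of one paragraph, with no added visits, tests or data.

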7.6.10 Pregnancy

If a female patient in the S-588410 Group becomes pregnant during the study, she must be instructed to discontinue all study drugs and inform the investigator immediately. All pregnancies that occur after the first dose of the study drug through the follow-up period must be reported within 24 hours of becoming aware of the pregnancy and the Pregnancy Form be faxed to the sponsor by the investigator (refer to 7.6.8.2, for reporting destination). Pregnancy complications and elective terminations for medical reasons must be reported as an AE or SAE as appropriate. Spontaneous abortions must be reported as an SAE. The outcome of the pregnancy should be followed by the study site and must be reported using the Pregnancy Form, which must be faxed to the sponsor. All pregnancies that are confirmed after the follow-up visit but within 6 weeks of last study drug dose should be reported to the sponsor. At the end of the pregnancy (ie, birth, miscarriage, abortion) for the patient, the outcome should be reported to the sponsor.

In addition, the investigator (or subinvestigator) must attempt to collect pregnancy information on any female partners of male patients in the S-588410 Group who become pregnant while the patient is enrolled in the study. Pregnancy information must be reported to the sponsor as described above.

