7.7 Withdrawal of Patients from the Study or Study Drug

The investigator or subinvestigator will make every reasonable attempt to complete the study. A patient may withdraw for any reason. The investigator or subinvestigator will advise the sponsor about the withdrawal of any patient.

The investigator will withdraw a patient from the study for any of the following reasons:

- When the investigator or subinvestigator determines that the patient is required to be initiated chemotherapy due to aggravation of the target disease.
- When the patient's PS (ECOG) becomes 3 or higher.
- When eosinophil counts are more than 5000/mm³
- When a definitive diagnosis of eosinophilic pneumonia or interstitial pneumonia is made and it is considered to be related to the study drug
- When the patient requests to be withdrawn from the study.
- When the patient is proved to be ineligible for the study after participating in the study.
- When the patient is lost to follow-up.
- When the patient should be withdrawn from the study based on the management and discontinuation criteria for liver function abnormalities ([Appendix 3](#)).
- When the investigator or subinvestigator determines that the patient should be withdrawn because of other reasons.

In the event of a patient's withdrawal, the investigator will promptly notify the sponsor and will make every effort to complete the early termination assessments. All patients withdrawn due to AEs will be followed until resolution of any AEs until the unresolved AEs are judged by the investigator to have stabilized, or the patient is lost to follow-up.

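### The Section 7.7 eosinophil bullet, and less clearly the liver bullet with Appendix 3, take a patient in either group out of the study when the action needed is to stop S-588410

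*Protocol*

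**What the plan says.** Section 7.7 has a heading that covers both the study and the study drug, but the sentence that governs its list has one outcome: "The investigator will withdraw a patient from the study for any of the following reasons". Three bullets matter here.

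- Eosinophils: "When eosinophil counts are more than" 5000/mm³. There is no group, no causal condition and no exemption.
- Pneumonia: "When a definitive diagnosis of eosinophilic pneumonia or interstitial pneumonia is made and it is considered to be related to the study drug". This bullet is limited to drug-related cases.
- Liver: "When the patient should be withdrawn from the study based on the management and discontinuation criteria for liver function abnormalities", with a reference to Appendix 3 and no group.

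The Appendix 3 list is headed "Drug Discontinuation Criteria Due to Abnormal Liver Chemistry Tests", and its governing sentence is "Patients must be discontinued from the study as described below except that the investigator judges abnormal liver chemistry test values are due to target disease" (the exception also requires that the investigator sees no need to discontinue). Earlier in the same appendix the first action is "Patients must be instructed to hold study medication immediately", and the re-start paragraph uses the list as the bar to resuming drug.

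Section 7.6.10 words a comparable rule by group and by drug: "If a female patient in the S-588410 Group becomes pregnant during the study, she must be instructed to discontinue all study drugs".

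**The concern.** Observation patients receive no drug (Section 5.4), so a drug-stopping rule has nothing to stop in them. Yet the operative words concern the study, and they apply to any patient. A site that follows the text would end an Observation patient's scheduled visits because of a laboratory value. That group is enrolled to supply tumor, PFS, OS and QOL data (Section 2.2). The same words take a treated patient off scheduled scans and questionnaires when stopping S-588410 could have been enough. At stake are completeness of centrally reviewed imaging, QOL and AE data for any such patient, and consistency between sites in applying a mandatory rule.

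**Working it through.** The plan states no figure on this point. The check is a reading of linked sections, plus a count of the schedule.

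**1. Can an Observation patient meet the criteria?** Yes. Section 7.4.6.1 applies routine laboratory tests to both groups. Table 7-2 includes the white-cell differential, AST, ALT and total bilirubin. Appendix 2 places these tests at Week 6, Week 12 and every 12 weeks after that. Section 7.4.6.1 refers to Section 7.6.7, which brings the Appendix 3 criteria into the review of abnormal results without naming a group.

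**2. Do the words limit the action to the drug or to treated patients?**

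| Text | Outcome in its operative words | Group or drug limit |
|---|---|---|
| 7.7, eosinophil bullet | out of the study | none |
| 7.7, pneumonia bullet | out of the study | drug-related cases only |
| 7.7, liver bullet | out of the study | none in the bullet |
| Appendix 3, discontinuation sentence | out of the study | none in the sentence; the heading says drug |
| 7.6.10, pregnancy | off the drug | S-588410 Group |

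The liver rule is therefore ambiguous, but its heading and the hold and re-start text largely resolve it as a drug rule. For the eosinophil bullet, the nearest pointer is Section 7.6.5, where the same count triggers extra tests in a section on expected drug reactions. Nothing in Section 7.7 itself limits it.

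**3. What stops and what continues after withdrawal?**

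- Scheduled tumor evaluation and QOL stop. Appendix 2 allows one set at discontinuation where feasible, and Table 7-3 gives it a 28-day window.
- Collection of new AEs stops at discontinuation (Section 7.6.2). Ongoing AEs are still followed (Sections 7.6.2 and 7.7).
- Survival, investigator-reported progression and subsequent therapy continue every 6 months (Section 7.3.3). Section 8.9.2 accepts investigator-reported progression in the PFS definition, though central-review PD has first priority.

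**4. Ceiling for one Observation patient (Appendix 2).**

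- Post-baseline scans: Weeks 12 to 96 every 12 weeks give (96 − 12)/12 + 1 = 8; adding Week 104 gives 9.
- Post-baseline QOL time points: these 9 plus Week 4 give 10.
- Withdrawn at the first on-study laboratory test (Week 6): at most 9 of 9 scans and 9 of 10 QOL time points remain to be lost.
- Withdrawn at Week 12, after that visit's assessments: at most 8 and 8.
- The discontinuation set may replace one time point.

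These are ceilings, reached only by a patient who would otherwise have stayed on schedule for all 104 weeks. An expected loss cannot be computed, because the protocol gives neither the frequency of these events nor the time on schedule.

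**The case against.** The strongest reply has four parts.

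**Context settles the liver rule.** The sentence sits under a drug-discontinuation heading, follows an instruction to hold medication, and serves as the bar to re-starting it. A reader might infer that Appendix 3 plainly orders untreated patients out of the study; the documents do not support so firm a reading. What stands is a mismatch between heading and operative sentence, repeated in the Section 7.7 liver bullet.

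**The eosinophil limit may be meant for everyone.** Exclusion criterion 10 applies the same 5000/mm³ limit at entry to both groups, so a group-neutral on-study rule could be deliberate. The contrast with the pneumonia bullet fits that reading too: a drug condition was added where one was wanted. For this reason the documents do not support saying that withdrawing an Observation patient serves no purpose.

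**Withdrawal frees the patient for treatment.** Section 6.2.1 prohibits most systemic corticosteroid and immunosuppressant use in both groups, and marked eosinophilia or hepatitis may call for it. This needs an answer in the fix, and the last bullet of Section 7.7 (other reasons, at the investigator's judgment) already provides one.

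**Staying on schedule off drug would need a new schedule.** This does not hold for the assessments at issue. Appendix 1 sets tumor evaluation, QOL and laboratory tests every 12 weeks from Visit 13, independently of dosing. Only vital signs and physical examination are tied to administration visits from Visit 14.

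**Conclusion.** The point holds as a minor wording defect, clearer for the eosinophil bullet than for the liver criteria. Read literally, a patient in either group who meets the values leaves scheduled central imaging, QOL and new AE collection, apart from one discontinuation set.

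The number affected is unknown, probably few and possibly none. Exclusion criteria 9 and 10 screen out high AST, ALT and eosinophil values at entry, most liver criteria require confirmation or persistence, liver values judged due to target disease can be exempted, and the Observation Group has at most 42 patients.

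Two larger conclusions might be inferred and are not supported. First, that PFS or OS in the Observation Group would be materially distorted: no event rate is given, OS and investigator-reported progression continue, and the protocol plans separate, descriptive estimates for each group with Observation survival curves labelled exploratory (Section 8.2). Second, that the primary result is at risk: CTL activity is not measured in the Observation Group, and for treated patients the protocol gives no basis for supposing that these criteria would remove many before Week 12.

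The conclusion rests on a literal reading of the operative sentences; a site that reads the liver criteria through their heading would not apply them to an untreated patient.

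**What to change.** In the eosinophil and liver bullets of Section 7.7 and in the Appendix 3 discontinuation sentence, replace withdrawal from the study with *permanent discontinuation of S-588410 (S-588410 Group)*.

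Add that patients in either group who meet these values stay on the existing 12-weekly tumor and QOL schedule and on AE collection until another Section 7.7 reason applies. State that a need for therapy prohibited under Section 6.2.1 counts as such a reason, through the bullet for other reasons.

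Leave the thresholds, the liver monitoring, the Liver Event Form and SAE reporting of Hy's law cases as they are.

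The cost is wording in two bullets and one sentence, plus the added statement. Observation patients need nothing beyond Appendix 2. The downside is continued scheduled assessments for the few treated patients who stop drug under these criteria.
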